- f) Following discharge patients only required to return for day 15, 22, 29, and 60 follow up visits unless they are discharged on study drug in which they will receive daily phone calls and will be required to have safety labs drawn as scheduled on days 3, 5, 8, 11 as applicable
- g) Day 1 is the first day of study drug
- h) Outpatient visits on day 5, 8, 11, 15, 22, 29, and 60 visits are preferred as in-person visits but may be done via telehealth and there is no need for vital signs or scheduled sample collection when telehealth is utilized unless outpatient labs can be requested via outside source (example Quest). Subjects with LFTs above 3x the ULN at enrollment will have LFTs checked daily during the hospitalization phase of the study.
- i) Outpatient adverse event monitoring will be performed via phone call
- j) Inpatient assessments will be done at the initial site of patient enrollment (NIH Clinical Center or Inova Health Systems.) After patient discharge, all outpatient assessments will be done at NIH Clinical Center, however laboratory can be done at non-NIH facility of patients who are having a telephone assessment.

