## 3 OBJECTIVES AND ENDPOINTS

The primary objective of this study is to evaluate the safety of fostamatinib for the treatment of hospitalized patients with COVID-19.

OBJECTIVES	ENDPOINTS	JUSTIFICATION FOR ENDPOINTS
Primary		
To assess the safety of fostamatinib in hospitalized patients with COVID-19	Cumulative incidence of SAEs through day 29.	This endpoint was chosen to evaluate the safety of fostamatinib for the treatment of hospitalized patients with COVID-19.
Secondary		

*Abbreviated Title: Fostamatinib for COVID*

*Version Date: 09/17/2020*

OBJECTIVES	ENDPOINTS	JUSTIFICATION FOR ENDPOINTS

To assess the effect of fostamatinib on clinically relevant endpoints of disease course
	
 
1. Time to recovery by day 29: day of recovery is defined as the first day on which the subject satisfies one of the following three categories: Ordinal scale 3: hospitalized, not requiring supplemental oxygen-no longer requiring ongoing medical care; Ordinal scale 2: non-hospitalized, limitations on activities and/or requiring home oxygen; Ordinal scale 1: non-hospitalized, no limitations on activities
 
2. Number of days free of mechanical ventilation [patients with baseline ordinal scale 5-6 only]
 
3. Mortality at day 14 and 28
 
4. Grade 3 and 4 AE through day 60
 
5. Days of hospitalization
 
6. Ordinal scale at day 15 and day 29
 
7. Change in CRP, IL-6, ferritin, d-dimer, fibrinogen, absolute lymphocyte count, absolute neutrophil count, and platelet count from baseline [day 3, 5, 8, 11, 15, 29]
 
8. Number of days in the ICU [entire hospitalization]
 
9. Relative change in PaO2/FiO2 or SpO2/FiO2 ratio
 
10. Change in SOFA score from baseline (day 1) [day 3, 5, 8, 11, 15, 29]
 
11. Number of days on oxygen (Including nasal canula, HFNC, non-invasive, and mechanical ventilation)
 
12. Days free of renal failure [entire hospitalization]
 
	
Each of the secondary clinical endpoints were deemed to be clinically relevant indicates for improved or worsening disease course

*Abbreviated Title: Fostamatinib for COVID*

*Version Date: 09/17/2020*

OBJECTIVES	ENDPOINTS	JUSTIFICATION FOR ENDPOINTS

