## **6.3 MEASURES TO MINIMIZE BIAS: RANDOMIZATION AND BLINDING**

### **6.3.1 Randomization**

The study will randomize subjects 1:1 to placebo or fostamatinib. Once a subject has completed the screening and baseline period and evaluation for inclusion/exclusion criteria, the randomization process will begin. The site investigator or designee will obtain the randomized assignment for that subject from the data coordinating center. Randomization will be stratified by site and severity of illness at enrollment. Severity of illness will be stratified into ordinal scale 5 and 6 (supplemental oxygen via nasal canula or non-invasive ventilation), mechanical ventilation, and ECMO.

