## **9 STATISTICAL CONSIDERATIONS**

### **9.1 SAMPLE SIZE DETERMINATION**

This study plans to enroll approximately 60 eligible subjects, randomized in a 1:1 ratio to fostamatinib or placebo.

The primary outcome of the study is cumulative incidence of SAEs through day 29. Because of data on safety of the fostamatinib in combination with standard of care is unavailable, the sample size is determined by the feasibility to assess the activity and safety of the study treatment in a diverse group of hospitalized adults. As background standards of supportive care may evolve/improve over time as more is learned about successful management of COVID-19, comparisons of safety will be based on data from concurrently randomized subjects between fostamatinib and placebo arm. Randomization is essential to evaluate the safety and early efficacy of fostamatinib, which may lead to generalizable evidence of future confirmative studies.

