4) Mortality rate and the time to event endpoints will be estimated by Kaplan-Meier method and 95% confidence intervals by study arm and compared between the treatment arms by log-rank test.

5) Longitudinal measurements of each biomarker variables will be plotted over time. The mean and percent change from baseline for each variable will be estimated and compared to study arm using appropriate parametric or nonparametric tests and regression modeling.

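### Section 9.3.3, item 5 does not commit the biomarker comparison to a log scale or to baseline adjustment, so power can be lost for skewed markers at about 30 patients per arm

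*Combined protocol and SAP*

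**What the plan says.** Secondary endpoint 7 in Section 3 is "Change in CRP, IL-6, ferritin, d-dimer, fibrinogen, absolute lymphocyte count, absolute neutrophil count, and platelet count from baseline", at days 3, 5, 8, 11, 15 and 29. That is 8 markers × 6 days = 48 marker-by-day comparisons.

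The analysis is item 5 of Section 9.3.3. Apart from plots over time, it says: "The mean and percent change from baseline for each variable will be estimated and compared to study arm". The sentence ends "using appropriate parametric or nonparametric tests and regression modeling". Nothing in the item names a scale, a baseline covariate, a repeated-measures structure, or a rule for choosing among the tests. Item 1 of the same section, on time to recovery, does state that its analysis is stratified by severity at enrollment.

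On size, Section 9.1 says: "This study plans to enroll approximately 60 eligible subjects, randomized in a 1:1 ratio to fostamatinib or placebo". It adds that "the sample size is determined by the feasibility to assess the activity and safety of the study treatment", so there is no power target for any marker. A footnote to the blood table in Section 8.2.2 requires the day 1 sample to be taken before the first dose, so a pre-treatment value is already planned.

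**The concern.** Item 5 names two outcome quantities, and both behave badly for a right-skewed concentration. A mean of raw changes is driven by the few patients with very high values. A mean of percent changes is driven by the few with very low baselines, because the baseline is the denominator.

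A change score also fixes the weight on the baseline at 1, whereas a model estimates it. With imperfect correlation this adds noise. It also carries part of any chance baseline difference between arms into the comparison.

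The stake is sensitivity. The rationale in Sections 2.2 and 2.3.3 is that the drug dampens inflammation and immunothrombosis, and these markers are where such activity would be seen. With about 30 per arm and a sample set by feasibility, the choice of analysis is one of the few places where power can be gained at no cost in patients.

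**Working it through.** The plan states no power, SD, correlation, effect or alpha for a marker, so there is no figure to reproduce. The check asks how far the permitted analyses differ under assumed values.

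**Inputs**
- From the plan: about 60 patients randomized 1:1, so n = 30 per arm (Sections 9.1 and 6.3.1).
- Assumed: log-normal marker; log SD 1; arm effect −0.65 on the log scale, so a geometric mean ratio of exp(−0.65) = 0.52; correlation ρ between log baseline and log follow-up of 0.3, 0.5 or 0.7; complete data; two-sided 5%.
- Assumed, and relevant only to raw change: both arms also fall by 0.5 on the log scale, to exp(−0.5) = 0.61 of baseline.

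**Step 1: formula on the log scale.** Log change has SD √(2(1−ρ)) = 1.18, 1.00, 0.77 at ρ = 0.3, 0.5, 0.7. ANCOVA has residual SD √(1−ρ²) = 0.95, 0.87, 0.71. The variance ratio is 2/(1+ρ) = 1.54, 1.33, 1.18. With noncentrality 0.65/(SD × √(2/30)), power is 55, 70, 89% for log change and 74, 82, 93% for ANCOVA.

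**Step 2: simulation (6,000 trials per row), power in %**

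| ρ | t, raw change | t, percent change | rank test, percent change | t, log change | log ANCOVA |
|---|---|---|---|---|---|
| 0.3 | 16 | 33 | 52 | 55 | 73 |
| 0.5 | 18 | 50 | 68 | 70 | 81 |
| 0.7 | 23 | 79 | 88 | 90 | 93 |

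The last two columns agree with Step 1 to within about 1 point. Type I error was 3 to 5.5% for all five analyses.

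**Step 3: loss against log ANCOVA, in points (ρ = 0.3, 0.5, 0.7)**
- Rank test on percent change: 73−52 = 21, 81−68 = 13, 93−88 = 5. A second set of runs gave 51, 67, 88%, so losses of 22, 14, 5. Range about 5 to 22.
- t-test on percent change: 40, 31, 14. The second set gave 34, 53, 80%, so losses of 39, 28, 13. Range about 13 to 40.
- t-test on raw change: 57, 63, 70.

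The raw-change figure depends on the assumed common fall. With no common change, simulated power is 26, 33, 46%, a loss of about 47 points throughout. With a common fall to half of baseline it is 12, 14, 16%, a loss of 61 to 77 points. The other columns do not depend on it.

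**Step 4: does any regression repair it?** Baseline-adjusted regression on untransformed percent change gives 38, 56, 82%, so adjustment without a change of scale recovers little. A baseline-adjusted regression on ranks of percent change (3,000 trials) gives 70, 78, 92% against 74, 80, 94% for log ANCOVA in the same runs, which is nearly all of it.

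**Step 5: where the loss shrinks or grows**
- Near-symmetric marker (log SD 0.3, ratio 0.8, ρ = 0.5): t on percent change 79%, untransformed ANCOVA 88%, log ANCOVA 90%. At ρ = 0.7: 95, 97, 97%.
- ρ = 0.9 (log SD 1, ratio 0.5): percent change and log ANCOVA are both at about 100%, so nothing is lost. Part of this is a ceiling. A t-test on raw change stays at 21%.
- 20 per arm (log SD 1, ratio 0.5, ρ = 0.5): t on percent change 38%, rank test 54%, log ANCOVA 68%. Fewer samples are plausible because a Section 1.3 footnote says "there is no need for vital signs or scheduled sample collection when telehealth is utilized", unless an outside laboratory can be used.

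**Step 6: baseline imbalance.** The standard error of a baseline difference is √(2/30) = 0.26 SD, so a difference of at least 0.25 SD has about a 33% chance for each marker. Unadjusted log change then shifts by (1−ρ) × 0.25 = 0.125 SD at ρ = 0.5, against an assumed effect of 0.65 SD.

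**The case against.** The strongest reply is that the sentence does not stop at mean and percent change. It goes on to allow suitable tests of either kind and regression. Regressing log change on arm and log baseline gives the same arm effect as log-scale ANCOVA, so the recommended model is already within the text. A reader might infer that the plan has chosen a t-test on raw or percent change and so gives up much of its power. The documents do not support that, because no such choice has been made.

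Skewness is also partly answered by a test the plan permits. Percent change is exp(log change) − 1, an increasing function, so a rank test gives the same result on either. That is why its power sits close to that of log change. What it leaves out is the baseline adjustment, which costs 5 to 22 points here.

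Three further points stand. The simulated data are log-normal, multiplicative and complete, all of which favour the log model. The eight markers include fibrinogen and three blood counts, and the documents do not say which markers are skewed. And a change score does use the day 1 value, so it would be wrong to say that the baseline is ignored.

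What the reply does not remove is that the quantities named for comparison remain mean and percent change. Some permitted routes, including a regression on untransformed percent change, recover little.

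**Conclusion.** The point holds as a missing commitment with a known better alternative. Item 5 names the less efficient quantities and leaves open whether they will be transformed or baseline-adjusted. If they are compared unadjusted, the loss for a strongly skewed marker runs from small (rank test, high correlation) to large (t-test on raw change), as set out in the working.

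The sizes are illustrative. They rest on an assumed log SD of 1, a ratio of 0.52 and correlations of 0.3 to 0.7. At log SD 0.8 to 1.2 with a ratio of 0.5, over the same correlations, the loss is about 1 to 20 points for the rank test and 3 to 40 for the t-test on percent change. They should not be read as the power of this trial, or as applying equally to all eight markers.

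A reader might also infer that the trial's main conclusion is at risk. It is not. The primary analysis is Fisher's exact test on SAEs (Section 9.3.2), and the plan makes no decision depend on a marker.

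**What to change.** In Section 9.3.3, item 5, state that the planned between-arm comparison is the log-transformed marker at each scheduled day, adjusted for the log day 1 pre-dose value and baseline severity. This can be ANCOVA by day, or one repeated-measures model with visit-by-arm terms. Report geometric mean ratios with 95% confidence intervals.

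For markers judged near-symmetric, the untransformed scale with the same baseline adjustment is acceptable. List those markers before unblinding. State how values below an assay limit enter the log scale. Keep mean and percent change as descriptive summaries.

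The cost is plan wording and minor programming. No new samples, visits or patients are needed.

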#### **9.3.4 Safety Analyses**

The planned analyses will also include descriptive statistics on the incidence and severity of adverse events. The proportions of serious adverse events (SAEs) will be summarized using sample proportions and confidence intervals for binomial distributions. Safety will be summarized using descriptive statistics to assess the difference between the two study arms. Summaries will be produced for all adverse events (AEs), related AEs (those considered by the Investigator as related to study treatment), SAEs, AEs leading to treatment discontinuation, and AEs Grade  $\geq 3$  in severity. Individual subject listings will be provided for any deaths, SAEs, AEs leading to interruption and AEs leading to treatment discontinuation for the fostamatinib arm compared to the placebo arm.

### **9.3.5 Baseline Descriptive Statistics**

Baseline characteristics will be summarized by treatment arm. For continuous measures the mean and standard deviation will be summarized. Categorical variables will be described by the proportion in each category (with the corresponding sample size numbers).

### **9.3.6 Planned Interim Analyses**

Interim safety analysis will be performed as requested by the by the NHLBI appointed, independent DSMB. Stopping guidelines will be evaluated if excess deaths or SAEs occur in the fostamatinib arm compared to the placebo arm. The number of interim monitoring looks and the stopping boundary based on the differences in the mortality rate and SAE between the two study arms will be developed and approved by the DSMB before the study enrollment. DCC will monitor the stopping boundary to alert DSMB if the stopping boundary is reached and have DSMB make further evaluation and recommendation about stopping the study due to safety reasons.

### **9.3.7 Sub-Group Analyses**

The following subgroups analysis will be performed.

- Symptoms duration >10 and ≤10 days
- Baseline disease severity
- Race (White, Black, Asian)
- Age (18 to <40, 40 to <66, ≥65)
- Sex (male and female)
- Concomitant therapies (e.g. treatment with and without remdesivir, steroids (dexamethasone, prednisone, hydrocortisone, methylprednisolone), convalescent plasma, tocilizumab or other immunomodulators intended for the treatment of COVID-19)
- Therapy with anti-coagulation by dose

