**Participant Duration:**

An individual subject will complete the study in a maximum of 60 days, from screening at Day -1 or 1 to follow-up through Day 60 ± 3 days.

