**Standard of Care:**

For the purposes of this study standard of care is defined primarily as remdesivir as an antiviral intended to decrease viral load and dexamethasone a broad-spectrum anti-inflammatory intended to dampen the immune response to SARS-CoV-2. However, it is noted that in the middle of a pandemic evidence for and against specific therapies for the treatment of COVID-19 continue to evolve and therefore standard of care may change throughout this study. At the current time once enrolled, use of any biologic therapy outside of local standard of care are prohibited. This includes monoclonal antibodies targeting cytokines (e.g., TNF inhibitors; interleukin-1[IL-1], IL-6 [tocilizumab or sarilumab]), or T-cells (e.g., abatacept); monoclonal antibodies targeting B-cells (e.g., rituximab in the last 6 months, and including any targeting multiple cell lines including B-cells); JAK inhibitor(s) other than baricitinib (e.g., imatibib, genfinitib); and interferon, plasma, or immunoglobulin (IgG) therapies for COVID-19 are not permitted. However, if patient has a clinical deterioration while on fostamatinib rescue therapies above including convalescent plasma may be considered. Additionally, if a specific site has a change in their standard of care outside of remdesivir and dexamethasone these medications will be permitted.

This study is randomized placebo-controlled study. All patients will receive standard of care described above.

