### **5.2 EXCLUSION CRITERIA**

1. ALT or AST  $> 5$  times the upper limit of normal (ULN) or ALT or AST  $\geq 3 \times$  ULN and total bilirubin  $> 2 \times$  ULN.  
Estimated glomerular filtration rate (eGFR)  $< 30$  ml/min
2. Pregnancy or breast feeding
3. Anticipated discharge in the next 72 hours
4. Allergy to study medication
5. Uncontrolled hypertension (systolic blood pressure  $> 160$  mmHg or diastolic blood pressure  $> 100$  mmHg)
6. Shock or hypotension at the time of enrollment
7. Neutrophil count  $< 1000/\mu\text{L}$
8. Concern for bacterial or fungal sepsis
9. Received immunomodulatory treatment within 30 days prior to enrollment e.g., Bruton's tyrosine kinase/phosphoinositide 3 kinase/Janus kinase inhibitor or cytokine-targeting biologic therapy (anti-TNF, IL-6), or B-cell depleting antibody in the prior 6 months (rituximab, other anti-CD20 mAb)
10. Received a live vaccine the last 4 weeks
11. Those who were cognitively impaired or mentally disabled prior to COVID diagnosis

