#### **6.5 CONCOMITANT THERAPY**

For this protocol, a prescription medication is defined as a medication that can be prescribed only by a properly authorized/licensed clinician. Medications to be reported in the CRF are concomitant prescription medications, over-the-counter medications and supplements used for the treatment of COVID-19.

For patients that are eligible for the study, other therapy received prior to enrollment with any other experimental treatment or off-label use of marketed medications that are intended as specific treatment for COVID-19 or the SARS-CoV-2 infection not identified in the exclusion criteria are permitted but must be discontinued on enrollment.

In patients who have clinical deterioration while on fostamatinib any rescue or investigational therapy that a provider thinks may benefit a patient may be administered (e.g. tocilizumab and convalescent plasma). Administration of these drugs will be tracked via the CRF.

Venous thromboembolism (VTE) prophylaxis is recommended for all patients unless there is a major contraindication such as active bleeding events or history of heparin-induced thrombosis.

Concomitant medications will be assessed only from 7 days prior to enrollment through discharge. Report all prescription medications taken during this time period.

*Abbreviated Title: Fostamatinib for COVID*

*Version Date: 09/17/2020*

Do not report vitamins, herbal supplements, or topical medications. Do not report over-the-counter cold medicines and antipyretics that the subject reportedly took at home prior to hospitalization.

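### Section 9.3.7 does not limit the co-therapy and anticoagulation subgroups to treatment in place at randomisation, so some form almost entirely afterwards; the age bands also overlap at 65

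*Combined protocol and SAP*

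**What the plan says.** Section 9.3.7 states that subgroup analyses will be carried out. Its list includes treatment with and without remdesivir, steroids, "convalescent plasma, tocilizumab or other immunomodulators intended for the treatment of COVID-19", and a separate item for anticoagulation by dose. Only disease severity in that list is labelled as a baseline factor. No dose categories, endpoint or test are given. The age bands are 18 to below 40, 40 to below 66, and 65 and over.

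Four other places bear on when these therapies can occur:

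- Section 6.5 gives the only recording window: "Concomitant medications will be assessed only from 7 days prior to enrollment through discharge".
- Section 5.2, item 9, excludes patients who "Received immunomodulatory treatment within 30 days prior to enrollment". Its examples include "Janus kinase inhibitor or cytokine-targeting biologic therapy (anti-TNF, IL-6".
- Section 6.5 says that, after clinical deterioration, "any rescue or investigational therapy that a provider thinks may benefit a patient may be administered (e.g. tocilizumab and convalescent plasma". The Standard of Care text in Section 4.1 also allows rescue on deterioration.
- The same Standard of Care text adds that "if a specific site has a change in their standard of care outside of remdesivir and dexamethasone these medications will be permitted". Its on-study prohibition covers "JAK inhibitor(s) other than baricitinib", which leaves baricitinib open.

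**The concern.** A subgroup supports a randomised comparison only if membership is fixed before treatment can influence it. If patients are grouped by what they received during the stay, the drug may help decide who is in each group. Section 2.3.3 hypothesises that fostamatinib reduces immune dysregulation and the organ failure that follows. If that is right, fewer treated patients deteriorate and fewer receive rescue. Those who still need it would be sicker on average than rescued placebo patients. The patients who avoid rescue on fostamatinib would then also include some who would have been rescued on placebo. Both groups could show a spurious excess of events on the drug. If the drug increased rescue, the sign would reverse.

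Anticoagulant dose raises the same issue. Dose can change after an event, and deep vein thrombosis or pulmonary embolism is itself secondary endpoint 13, so a dose group could be defined partly by an outcome.

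The age overlap is simpler: a patient aged 65 is counted in both the middle and the oldest band.

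**Working it through.** **When the groups form.** The recording window covers the 7 days before enrolment and then the stay to discharge. Exclusion 9 reaches back 30 days, so the pre-enrolment part of the window holds no anti-IL-6 agent or Janus kinase inhibitor in an eligible patient. Any such use comes later: as rescue, through a changed site standard of care, or, for baricitinib, through the exception.

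One narrow gap is conceivable. The Synopsis describes participation "from screening at Day -1 or 1 to follow-up through Day 60". If enrolment meant consent on Day -1, use could begin in the roughly one day before randomisation. Section 9.3.3 ties enrolment to the start of study drug, and footnote b in Section 1.3 allows consent the day before enrolment, so the text points away from that reading.

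Remdesivir, steroids, convalescent plasma and anticoagulants can be in place at baseline. For these the fault is the missing time limit.

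**Possible size.** The plan has no figure to reproduce. About 30 per arm follows from Section 9.1 (60 patients, 1:1); everything else here is assumed.

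- Severity U ~ N(0,1), with slope s = 1.2, 2 or 3.
- Rescue: logit = a + sU + ln(OR) × drug, with a set so that 20% to 40% of placebo patients are rescued.
- SAE: logit = b + sU in both arms, with b set for 30% overall. The drug has no effect on SAEs.
- SAE rate among the rescued = E[P(rescue|U) × P(SAE|U)] / E[P(rescue|U)]; the not-rescued rate uses 1 − P(rescue|U).
- SE = √(p₁(1−p₁)/n₁ + p₀(1−p₀)/n₀), with n = 30 × the group's share of the arm.

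Example with s = 3, OR 0.37 and placebo rescue 40%. Rescued patients number 30 × 0.40 = 12 on placebo and 30 × 0.295 = 8.85 on fostamatinib. Their SAE rates are 59.0% and 67.1%, a spurious +8.1 points. SE = √(0.590 × 0.410/12 + 0.671 × 0.329/8.85) = 21.2 points, so the ratio is 8.1/21.2 = 0.38.

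Artefact in percentage points, fostamatinib minus placebo:

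| s | OR 0.37–0.5, rescued | OR 0.37–0.5, not rescued | OR 2–2.7, rescued | OR 2–2.7, not rescued | Largest ratio to SE |
|---|---|---|---|---|---|
| 1.2 | +2.8 to +4.5 | +1.5 to +2.9 | −3.0 to −4.5 | −1.9 to −3.1 | 0.23 |
| 2 | +4.6 to +7.2 | +2.3 to +3.9 | −4.7 to −7.2 | −2.6 to −3.9 | 0.34 |
| 3 | +4.7 to +8.1 | +2.6 to +4.0 | −5.3 to −8.1 | −2.4 to −4.0 | 0.40 |

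At OR 1 the artefact is 0 throughout. In the table's settings the SEs are 18 to 36 points (rescued) and 10 to 15 points (not rescued). Varying the SAE rate from 20% to 50% raises the largest values to 8.8 points and 0.41 SE.

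A second, threshold-type model shows how far the size depends on assumptions. It takes SAE 25% and placebo rescue 30%, with the drug lowering latent deterioration by 0.25 to 0.75 SD. When prognosis and deterioration correlate at 0.5, the artefact is +3.1 to +9.9 points in the rescued and +1.5 to +3.9 in the not rescued. At 0.8 it is +5.9 to +17.7 and +2.4 to +6.8. At the extreme:

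- Rescued, 52.7% of 9 against 70.4% of 3: SE = √(0.527 × 0.473/9 + 0.704 × 0.296/3) = 31.2 points; 17.7/31.2 = 0.57.
- Not rescued, 13.1% of 21 against 19.9% of 27: SE = √(0.131 × 0.869/21 + 0.199 × 0.801/27) = 10.6 points; 6.8/10.6 = 0.64.

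**Age.** Checking each whole-number age from 18 to 100 against the printed bands, 65 is the only one not in exactly one band, and there are no gaps. If 1% to 4% of patients are 65 (assumed), the expected number counted twice is 60 × 0.01 = 0.6 to 60 × 0.04 = 2.4. The chance of at least one is 1 − 0.99⁶⁰ = 45% to 1 − 0.96⁶⁰ = 91%.

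**The case against.** The best case for leaving the text alone is that little rests on it. The artefact vanishes if the drug does not alter rescue, it is well under one standard error in every setting tried, and the sample size is set by feasibility. No stated decision depends on Section 9.3.7. That section also never cites the Section 6.5 window and names no arm comparison, so the analyses might be meant as baseline or purely descriptive ones. The age overlap is probably a typing slip.

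Much of this stands. Bias is conditional, and reading these as comparisons of arms over the whole recorded window is an inference, though the natural one. It does not remove the point. A baseline reading would leave the tocilizumab group essentially empty, so its listing makes sense only with later use. Noise does not make a non-randomised contrast interpretable, and Section 9.1 looks ahead to confirmatory studies. Blinding stops knowledge of the arm from driving rescue, but not a drug effect on deterioration.

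A fair further objection is that, in a safety trial, readers will want to see events among patients given each co-therapy. A descriptive table can meet that need.

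**Conclusion.** The concern holds. Section 9.3.7 sets no time limit on the therapy subgroups and no other section supplies one. The tocilizumab-type groups form essentially only after randomisation, and the age bands overlap at 65. These conclusions follow from the text and do not depend on the modelling.

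The size of any bias does depend on assumptions: a link between severity and both rescue and SAEs, and a drug effect on rescue. The figures are illustrations, not bounds, and the artefact is small against sampling error at 60 patients. The primary analysis (Sections 9.2.2 and 9.3.2) is untouched. The text should be corrected, but the point does not threaten the trial's main result.

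**What to change.** In Section 9.3.7:

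- Define the remdesivir, corticosteroid, convalescent plasma and anticoagulant-dose subgroups by therapy received or in place at or before randomisation, and before first study drug.
- Prespecify the anticoagulant dose categories; the sponsor chooses them.
- Do not compare arms within groups defined by tocilizumab or other agents that exclusion 9 keeps out before enrolment. If any such use starts between consent and randomisation, list it as baseline use.
- Report use of every listed therapy after randomisation descriptively by arm (number of patients, study day of first use), labelled as non-causal. A table of SAEs by co-therapy and arm, labelled as non-randomised, is a reasonable optional addition.
- Use one cut-point, of the sponsor's choice, between the two upper age bands.

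Naming the endpoint and method for the subgroup analyses in the same edit would close a related gap.

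The cost is a wording amendment, which needs IRB approval before use (Statement of Compliance). Section 6.5 already collects medication from 7 days before enrolment and tracks rescue drugs on the CRF, but does not say that dose is recorded. The sponsor must check that baseline anticoagulant dose is captured, and change the CRF if it is not. The comparison of arms with and without rescue is given up; it has no randomised interpretation.
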